Myxofibrosarcoma (MFS) represents one of the most common sarcomas in the adult / elderly age and its incidence is increasing due to the increase in the average age of the population; mainly affects the limbs and limbs, especially the lower limb. When compared to other histotypes, the typical feature of MFS is the tendency to a greater risk of local recurrence (RL) regardless of the degree of histological malignancy and surgical margins (60% vs. 25-30%)(1). Such local aggression could be caused by the specific histological pattern of infiltrative growth. Local recurrence is also characterized by a variable, but high (15–38%) progression of degree, thus increasing the metastatic potential at the time of any local relapse (2). The use of local (radiotherapy) or systemic (chemotherapy) adjuvant therapies have not shown efficacy in terms of increasing the control of local and / or systemic diffusion. Despite this, the prognosis of MFS is relatively good with a metastasis rate of 20-25% and an estimated survival of approximately 75% at 5 years and 70% at 10 years(3). Morphologically, it appears as a tumor with distinctive characteristics (association of hypocellular mixoid areas and hypercellular fibrous areas); however, it does not have a specific immunohistochemical pattern, so the histological diagnosis is mainly based on the hematoxylin-eosin morphology (4). MFS is characterized by nonspecific cytogenetic aberrations and complex and unbalanced karyotypes, which increase with increasing degree, suggesting a multi-step tumor progression process due to the acquisition of genetic instability (5). Recently, Heitze et al. in a series of 25 cases of MFS (grade 1 and 3) they identified some genes with amplified expression including CCND1, CCNE1, EGFR, PTEN, RET (MET) and some deleted genes including TP53 and RB1. The mutation analysis also highlighted the presence of somatic mutations in TP53, PTEN, FGFR3, CDKN2A, and RB1 (6).

However, for none of these alterations has a correlation been observed with the prognosis (in terms of overall or progression-free survival). On this basis, knowledge of genetic changes appears essential for the identification of potential biomarkers useful both at diagnostic / prognostic and therapeutic level.

OBJECTIVE OF THE STUDY

The aim of the present study, in a serie of patients with a diagnosis of Mixofibrosarcoma treated at the Rizzoli Institute from *1 January 1993 up to 01 December 2017*, is to identify patients with different risk classes in terms of disease-free survival (local and systemic recurrence) and total survival. The study will exam all the clinical, radiological, histological and immunohistochemical features of this tumour in all samples and in a limited serie of cases the presence of mutation of 50 genes cancer related.

STUDY DESIGN

To identify patients with different risk classes in terms of disease-free survival (local and systemic recurrence) we will review about 200 cases of mixofibrosarcoma of extremities treated at our institution. We will perform immunohistochemical and molecular analysis by NGS, Sanger sequencing and Digital PCR considering 50 cancer-related genes. Survival analysis for disease free-survival and overall survival was carried out using Kaplan-Meier curves and log-rank tests.

POPULATION

Inclusion criteria

- 1) Male and female patients treated at Rizzoli Institute from 01 Jan 1993 to 01 Dec 2017
- 2) Diagnosis of mixofibrosarcoma of extremities
- 3) Histological slides/formalin-fixed paraffin-embedded tissue tumor (FFPE) blocks from archive available to perform the histology analysis and molecular analysis
- 4) Enough tumor biobanked material available for molecular analysis
- 5) Presence of the biobank signed informed consent
- 6) Written informed consent prior to any study-specific analysis and/or data collection

Exclusion criteria

- 1) Patients with histological diagnosis different from mixofibrosarcoma of extremities

MATERIAL AND METHODS

We will retrieve from the database of the Rizzoli institute all the cases with a histological diagnosis of mixofibrosarcoma of the extremities from 01 Jan 1993 to 01 Dec 2017

We aspect to find approximately 200 cases.

We will review all the medical records, radiological imaging, and histological data of these cases.

The immunohistochemical analysis of the principal altered genes identified in this tumor by the literature will be performed. In a limited serie of cases, we will perform NGS analysis of specific hot spot mutations cancer-related in 50 genes. Results obtained will be validated by Sanger sequencing and Digital-PCR in all the selected cases.

STATISTICS

To the case series will be applied a descriptive statistic.

DATA COLLECTION

Clinical data will be retrieved by patient charts.

A protocol-specific CRF reporting the results of the review will be provided.

A CRF is required and should be completed for each included subject.

ETHICS AND QUALITY ASSURANCE

The clinical trial protocol and its documents will be sent before initiating the study to the competent Authorities and Ethics Committees of each participating country for its approval.

The responsible investigator will ensure that this study is conducted in agreement with either the most updated Declaration of Helsinki and all the international and local laws that apply to clinical trials and to patient protection.

The protocol has been written, and the study will be conducted according to the principles of the ICH Harmonized Tripartite Guideline for Good Clinical Practice

(ref: <http://www.emea.eu.int/pdfs/human/ich/013595en.pdf>).

INFORMED CONSENT

All patients will be informed, by the investigator, of the aims of the study, the possible risks and benefits that will derive from the study participation.

The Investigator must clearly inform that the patient is free to refuse participation in the study and that can withdraw consent at any time and for any reason.

They will be informed as to the strict confidentiality of their patient data, but that their medical records may be reviewed for trial purposes by authorized individuals other than their treating physician.

The informed consent procedure must conform to the ICH guidelines on Good Clinical Practice. This implies that "the written informed consent form should be signed and personally dated by the patient or by the patient's legally acceptable representative".

The Investigator must also sign the Informed Consent form, and will keep the original at the site and a copy of the original must be handed to the patient.

The competent ethics committee for each Institution participating to the study must validate local informed consent documents before the study can be opened. It will be emphasized that the participation is voluntary and that the patient is allowed to refuse further participation in the study whenever he/she wants. This will not prejudice the patient's subsequent care.

Due to the high incidence of mortality of the disease under investigation, it would be possible that some potential eligible subjects will be deceased.

GENERAL PRINCIPLES FOR HUMAN BIOLOGICAL MATERIAL (HBM) COLLECTION

Human biological material (HBM) collection involves the collection and storage of biological material, residual biological material or derivatives in compliance with ethical and technical requirements.

Biological material (FFPE blocks and frozen tissue of tumor sample) are already stored in the archive of the Istituto Ortopedico Rizzoli, Pathology Department.

The biological material will be used and stored according with the sample characteristic and applicable regulation.

- The Istituto Ortopedico Rizzoli will have a designated person responsible for collection and will act as a communication point
- The collected HBM should be documented, i.e. the amount remaining and its location. act as a communication point

CONFIDENTIALITY

In order to ensure confidentiality of clinical trial data as disposed the national and European applicable regulation, data will be only accessible for the trial Sponsor and its designees, for monitoring/auditing procedures, the Investigator and collaborators, the Ethics Committee of each corresponding site and the Health Authority.

Investigator and the Institution will allow access to data and source documentation for monitoring, auditing, Ethic Committee revision and inspections of Health Authority, but

maintaining at all times subject personal data confidentiality as specified in the “Directive 95/46/EC of the European Parliament and of the Council of 24 October 1995”.

The Investigator must guarantee that patient anonymity is kept at all times and their identity must be protected from unauthorized persons and institutions.

All patients included in the study will be identified with a numeric code, so that no identifiable personal data will be collected (pseudo anonymization)

The Investigator must have and conserve a patients' inclusion registry where it figures the personal data of the patient: name, surname, address and corresponding identification code into the study, this register will be kept on the Investigator File.

PUBLICATION OF RESULTS

The results from this study will be published or shown at scientific conferences.

The final publication of the study results will be written by the Principal Investigator.

SPONSOR ROLE AND RESPONSIBILITY

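### The only inferential methods the protocol names compare groups, so measured features must be cut before testing; a single cut can lose a third or more of their information, and no cut is fixed

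*Protocol*

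**What the plan says.** The aim, under OBJECTIVE OF THE STUDY, "is to identify patients with different risk classes in terms of disease-free survival (local and systemic recurrence) and total survival". The candidate features are broad: "The study will exam all the clinical, radiological, histological and immunohistochemical features of this tumour in all samples". Mutation data on 50 genes are added for a limited number of cases.

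For linking features to outcome, STUDY DESIGN gives one sentence: "Survival analysis for disease free-survival and overall survival was carried out using Kaplan-Meier curves and log-rank tests". The STATISTICS section adds only this: "To the case series will be applied a descriptive statistic". The protocol names no regression model, no cut-point and no number of groups.

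The series is a closed archive from 1993 to 2017. On its size, MATERIAL AND METHODS says: "We aspect to find approximately 200 cases". That is an expected count, not a calculated sample size.

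**The concern.** The protocol chooses a method here; it does not defer the choice. Kaplan-Meier curves and the log-rank test work on groups, so a feature recorded on a scale can enter neither until someone divides it.

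Two things are at stake. First, cutting discards information in a series that cannot be enlarged, so a feature that does carry prognosis is more likely to be missed. Second, the data are retrospective and no cut is written down, so nothing stops a cut from being picked because it separates the curves. That would bring features with no effect into the risk classes. Both errors bear directly on the study's aim.

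**Working it through.** The protocol gives no significance level, power, effect size or event target, so there is no figure of its own to reproduce.

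**Inputs from the protocol**
- About 200 cases (MATERIAL AND METHODS).
- From the opening background section, "estimated survival of approximately 75% at 5 years and 70% at 10 years". This gives roughly 200 × 0.25 = 50 to 200 × 0.30 = 60 deaths.
- From the same section, 60% local recurrence, or roughly 200 × 0.60 = 120 disease-free survival events.

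**Assumptions, not in the protocol**
- Some features are measured on a scale (age, tumour size, percentage of stained cells).
- The effect on the log hazard is linear, with a hazard ratio of 1.4 per standard deviation (SD) for power.
- Tests are two-sided at 0.05.

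**1. Information kept by one cut of a normal feature, small effect.** With share p on one side, the proportion kept is φ(z_p)² / [p(1 − p)].

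| Cut | Kept | Lost |
|---|---|---|
| 50/50 | 0.637 | 36% |
| 25/75 | 0.539 | 46% |
| 20/80 | 0.490 | 51% |

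At the median, 200 × 0.637 ≈ 127, so the feature is tested as if about 73 of 200 patients had been dropped.

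**2. How far this depends on the assumptions**
- *Shape.* A median cut loses 25% for a uniform feature, 52% for an exponential one and 53% for a log-normal one (log-SD 0.6).
- *Number of groups.* Three, four and five equal groups of a normal feature lose 21%, 14% and 10%.
- *Direction of an uneven cut.* The 51% at 20/80 is a small-effect figure. At a hazard ratio of 1.4 per SD, the feature's mean among those with events shifts by ln 1.4 = 0.336 SD. If the cut isolates the highest-risk fifth, that fifth holds 30.7% of events, and (0.307 − 0.200)² / 0.16 / 0.336² ≈ 0.63 is kept. If it isolates the lowest-risk fifth, that fifth holds 11.9% of events, and (0.200 − 0.119)² / 0.16 / 0.336² ≈ 0.36 is kept. The loss is then about 37% or 64%, with 51% in between.

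**3. Power.** Uncut: Φ(√D × ln 1.4 − 1.96), where D is the number of events. Median cut: the same with D × 0.637. Tertiles, unordered: non-central chi-square on 2 degrees of freedom with non-centrality D × 0.793 × (ln 1.4)².

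| Events | Uncut | Median cut | Tertiles, unordered |
|---|---|---|---|
| 50 | 66% | 48% | 46% |
| 60 | 74% | 55% | 54% |
| 120 | 96% | 84% | 84% |

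For 60 events: √60 × 0.336 − 1.96 = 0.65, so Φ = 74%; √38.2 × 0.336 − 1.96 = 0.12, so Φ = 55%. Tertiles keep more information, but the second degree of freedom uses up the gain. A simulation of 200 cases with about 64 deaths gave 76% uncut against 55% at the median.

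**4. Searching for a cut.** In simulated series of 200 with no effect and 30% or 60% events, taking the best of 17 cuts between the 10th and 90th percentiles gave p < 0.05 in about 30% of series (30% to 32% across runs). The best of three cuts (both tertiles and the median) gave 11% to 12%. A single cut fixed in advance stays near 5%.

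**The case against.** The strongest reply is that the sentence on methods is not exclusive. It rules out no regression model and prescribes no cut. Coding of covariates and choice of models commonly sit in a statistical analysis plan, which may exist but is not available here. Comparing risk classes is also what Kaplan-Meier curves and log-rank tests are for, and classes could be formed from a score built on uncut features.

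Much of this stands, and it limits what can be claimed. A reader might infer any of the following, and the protocol supports none of them:

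- *That the protocol forces a loss of a third to a half on every measured feature.* It fixes no two-way split. The loss depends on the number of groups, the position of the cut and the shape of the feature.
- *That age, tumour size and staining percentage are planned variables.* They are assumed examples; the protocol names only broad families of features. For mutation present or absent there is nothing to cut.
- *That grade will be tested as if unordered.* A log-rank test for trend is a log-rank test and fits the sentence as written.
- *That cuts will be chosen by looking at outcome.* No such search is proposed. It is only not prevented, and 30% belongs to an extensive one.

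What the reply does not remove is that a method has been chosen. The only inferential tools named cannot take a measured feature uncut, and an analysis plan that followed the sentence literally would inherit the limitation.

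**Conclusion.** The point holds in conditional form. It is a weak choice of method, not an error of fact, and it should be changed before outcomes are linked to features.

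For a roughly normal feature with a log-linear effect, one cut loses about 36% of the information at the median and about 51% at 20/80. Across plausible shapes, a median cut loses from about 25% to just over 50%. At 60 deaths and a hazard ratio of 1.4 per SD, the cost is about 19 percentage points of power (74% to 55%), and unordered tertiles do not recover it. With about 120 events the cost is smaller, about 12 points (96% to 84%). The event counts are rough, since they apply background rates to an expected number of cases. The inflation of the false-positive rate is a risk left open, with a size set by how many cuts are tried.

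**What to change.** In STUDY DESIGN, add that:

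- features measured on a scale are tested and reported uncut in Cox regression, linear by default, with the linearity assumption checked;
- ordered features such as histological grade are tested by a log-rank test for trend;
- Kaplan-Meier curves and log-rank tests are kept for categorical features and for displaying the final risk classes;
- any cuts used are fixed before outcomes are linked to features.

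Bring the STATISTICS section into line at the same time, because a purely descriptive analysis sits poorly with log-rank testing. Flexible curves for every feature are not needed: with about 50 to 60 deaths they would use up scarce degrees of freedom.

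The cost is a few sentences and a little programming on data already in the archive. The downsides are single-feature results that are slightly less simple to read, and reliance on a linearity assumption that has to be checked.

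### Log-rank tests without adjustment for grade cannot show that a marker is prognostic beyond grade, although the Protocol's own background links chromosomal aberrations to grade

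*Protocol*

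**What the plan says.** The Objective section says that the aim "is to identify patients with different risk classes in terms of disease-free survival (local and systemic recurrence) and total survival". Clinical, radiological, histological and immunohistochemical features are to be examined in all samples, and 50 genes in a subset whose size is not given.

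The Study Design section describes the immunohistochemical and molecular work and then names the only inferential method in the document: "Survival analysis for disease free-survival and overall survival was carried out using Kaplan-Meier curves and log-rank tests". The Statistics section adds one sentence: "To the case series will be applied a descriptive statistic". Neither mentions strata, covariates or a multivariable model.

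The background text at the start of the Protocol makes three statements about grade:

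- On aberrations: "MFS is characterized by nonspecific cytogenetic aberrations and complex and unbalanced karyotypes, which increase with increasing degree".
- On systemic outcome, it describes a "progression of degree, thus increasing the metastatic potential at the time of any local relapse".
- On local outcome, it describes a "greater risk of local recurrence (RL) regardless of the degree of histological malignancy and surgical margins".

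It justifies the genetic work by the search for biomarkers with diagnostic, prognostic or therapeutic use, and notes that the alterations reported so far had not correlated with prognosis.

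**The concern.** A factor that is related both to a marker and to outcome confounds a crude comparison of marker groups. The background supplies the first link for cytogenetic aberrations and karyotypes. It supplies part of the second by tying grade progression to metastatic potential. If both links hold for a marker under study, its Kaplan-Meier curves will separate even when the marker says nothing that grade does not already say.

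The stake is the reading of a positive result. Since earlier alterations are reported as unrelated to prognosis, a significant log-rank test here would be taken as a new prognostic biomarker. Risk classes built on it could largely restate the histological grade.

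**Working it through.** The Protocol gives no significance level, effect size or event count, so there is no stated figure to reproduce. The check is a simulation of a marker with no effect of its own.

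**Inputs from the Protocol**
- Overall survival of 75% at 5 years and 70% at 10 years.
- About 200 cases.

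**Assumptions, not in the Protocol**
- 60% of tumours are high grade.
- The grade hazard ratio (HR) is 1, 1.5, 2 or 3.
- Marker prevalence in high/low grade is 40%/40%, 40%/20% or 50%/10%.
- Censoring is uniform over 3 to 15 years.
- The sequenced subset has 50 cases.
- Tests are two-sided at 5%.

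**Step 1. Why the groups differ.** By Bayes' rule, the high-grade share is as follows.
- Prevalence 50%/10%: marker-positive 0.6×0.5/(0.6×0.5 + 0.4×0.1) = 0.30/0.34 = 88%; marker-negative 0.30/0.66 = 45%.
- Prevalence 40%/20%: marker-positive 0.24/0.32 = 75%; marker-negative 0.36/0.68 = 53%.

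At time zero, the apparent marker HR is [1 + s₁(HR−1)]/[1 + s₀(HR−1)], where s₁ and s₀ are these shares. With a grade HR of 2 it is 1.882/1.455 = 1.29 and 1.750/1.529 = 1.14. With a grade HR of 3 it is 2.765/1.909 = 1.45 and 2.500/2.059 = 1.21. The true marker effect is 1 in every case.

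**Step 2. Survival model.** Marginal survival is S(H) = 0.4·exp(−H) + 0.6·exp(−H·HR). Solving S(H₅) = 0.75 and S(H₁₀) = 0.70 gives low-grade hazards of H₅/5 in years 0 to 5 and (H₁₀−H₅)/5 afterwards.

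**Step 3. Tests.** At each event, g is 1 if the patient carries the marker, and p is the share of carriers at risk. The unadjusted test compares [Σ(g−p)]²/Σp(1−p) with 3.8415. The stratified test computes both sums within grade and adds them before dividing.

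**Step 4. Results.** 6,000 data sets per row; the Monte Carlo standard error at 5% is √(0.05×0.95/6000) = 0.28 percentage points.

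| N (mean deaths) | Prevalence high/low | Grade HR | Unadjusted | Stratified |
|---|---|---|---|---|
| 200 (about 57) | 40%/20% | 1.5 | 7.0% | 5.1% |
| | | 2 | 8.8% | 5.2% |
| | | 3 | 12.9% | 5.0% |
| | 50%/10% | 1.5 | 10.0% | 5.1% |
| | | 2 | 18.0% | 4.8% |
| | | 3 | 32.3% | 5.2% |
| 50 (about 14) | 40%/20% | 1.5 | 5.9% | 5.7% |
| | | 2 | 5.9% | 4.6% |
| | | 3 | 7.1% | 4.8% |
| | 50%/10% | 1.5 | 6.9% | 5.0% |
| | | 2 | 9.0% | 5.1% |
| | | 3 | 12.6% | 4.9% |

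**Step 5. Control.** With a grade HR of 1, or with prevalence 40%/40%, the unadjusted test rejects in 4.6% to 5.4%. The excess therefore needs both links and is due to confounding.

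**The case against.** The strongest reply is that the stated aim is to find risk classes, not to prove value independent of grade. A crude log-rank test asks whether two marker groups differ in survival. If the marker tracks a prognostic grade, they do differ, and rejection is a correct answer. The rates above are errors only against the hypothesis of no effect given grade, which the Protocol does not state. This stands, so the crude analysis can be kept as description. It does not cover the further step, invited by the background, of calling a marker a prognostic biomarker.

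A second reply is that a log-rank test named without strata may be stratified in an analysis plan that is not shown. That is possible. The point is limited to the method this document names, set beside its own background.

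Several stronger readings are tempting but unsupported:

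- **Grade will not be used.** Histological features are to be examined in all samples, and grade is one of them. Nothing says it is left out.
- **The gene and immunohistochemical markers are known to track grade.** The background says this of cytogenetic aberrations and karyotypes only. Extending it to hot-spot mutations or protein markers is plausible but not stated.
- **Grade at diagnosis is stated to affect survival.** The text speaks of grade progression and metastatic potential at local relapse. The effect on survival is inferred.
- **Disease-free survival is hit harder.** If grade acts on every event, with an assumed 5-year disease-free survival of 50% and N=200, the unadjusted test rejects in 8.4% to 69.5% over the same grade hazard ratios and the two unequal prevalence patterns. But the background describes the raised local recurrence risk as independent of grade and puts local recurrence at 60% against 20% to 25% for metastasis. Many events would then carry no grade effect, so these rates should not be used.
- **The N=200 rates apply to the gene panel.** Sequencing is limited to a subset, so the smaller N=50 rates are the nearer guide there.

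**Conclusion.** The concern holds in a limited form. The named method suits a crude description of risk classes but cannot support a claim that a marker is prognostic beyond grade. The possible excess of false claims for overall survival runs from slight (about 6%, small subset, weak links) to substantial (about 32%, all 200 cases, strong links), against a nominal 5%. The grade hazard ratio, grade mix, marker prevalences, censoring and subset size are all assumed, and the excess vanishes if either link is absent. The concern applies mainly to systemic recurrence and overall survival, and least to local recurrence. It is a worthwhile and inexpensive improvement, not a defect that invalidates the study.

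**What to change.** Keep the Kaplan-Meier curves and crude log-rank results, labelled as descriptive. For each immunohistochemical or gene marker, add a log-rank test stratified by reviewed histological grade, or a Cox model with grade as a covariate. State that a marker will be called prognostic beyond grade only on that adjusted result. Fix the choice of method and the grade categories before markers are compared with outcome.

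The cost is small. Histological data are already to be reviewed for all cases, so no new patients or material are needed, only a short addition to the analysis text and code. The price is somewhat lower precision in the small sequenced subset, where about 14 deaths (if it has 50 cases) would be divided between grade strata.

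### Inclusion items 3 and 4 require tissue for molecular analysis from every patient, although mutation analysis appears to be planned only for a limited series

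*Protocol*

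**What the plan says.** The Population section of the Protocol gives six inclusion criteria as one cumulative list, with no separate list for a molecular subset. Item 3 asks for slides or "blocks from archive available to perform the histology analysis and molecular analysis". Item 4 adds a quantity condition: "Enough tumor biobanked material available for molecular analysis". Items 5 and 6 concern consent.

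The Objective of the Study sets two levels of work. Clinical, radiological, histological and immunohistochemical features are examined "in all samples and in a limited serie of cases the presence of mutation of 50 genes cancer related". Material and Methods repeats the limit for sequencing: "In a limited serie of cases, we will perform NGS analysis of specific hot spot mutations cancer-related in 50 genes". The next sentence reads "Results obtained will be validated by Sanger sequencing and Digital-PCR in all the selected cases". Study Design states no limit: "We will perform immunohistochemical and molecular analysis by NGS, Sanger sequencing and Digital PCR considering 50 cancer-related genes".

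On numbers, Material and Methods describes a database search by diagnosis, site and dates and then says "We aspect to find approximately 200 cases". It continues: "We will review all the medical records, radiological imaging, and histological data of these cases". The section on human biological material says that FFPE blocks and frozen tissue are already in the archive, without saying for how many cases or whether the amount is enough for molecular work.

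**The concern.** The main aim is to find risk classes for disease-free and overall survival, analysed with Kaplan-Meier curves and log-rank tests. A patient outside the molecular series contributes to that aim through follow-up, imaging, histology and immunohistochemistry. None of these needs the quantity of material that item 4 demands. Yet such a patient is ineligible if too little tissue remains for sequencing or PCR.

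Two things are at stake. The survival cohort can be smaller than it needs to be. And if having enough stored tumour is related to prognosis, the risk classes are derived in a selected group. The Protocol gives nothing from which the size or direction of such selection could be judged. Eligibility is also not something a statistical analysis plan could repair later, because it cannot bring back patients who were never included.

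**Working it through.** **1. The sections side by side**

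| Place in the Protocol | Who needs molecular-grade tissue or gets the assay |
|---|---|
| Inclusion item 3, molecular part | every patient |
| Inclusion item 4 | every patient |
| Objective | a limited series (mutations in 50 genes) |
| Material and Methods, NGS sentence | a limited series |
| Material and Methods, validation sentence | unclear: the NGS series, or all included cases |
| Study Design | no limit stated |

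The validation sentence directly follows the NGS sentence and speaks of validating results already obtained. NGS results exist only for the limited series, so that series is the natural referent. The Objective also limits mutation analysis itself, not NGS alone. The wider meaning is possible but fits the text less well.

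**2. What the 200 counts**

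No sample-size formula lies behind the figure, so there is nothing to reproduce. It is the expected yield of a search on diagnosis, site and dates, and it is not shown to be the number meeting items 3 to 6.

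**3. Illustration of the loss in precision**

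The documents give no retention rate, so a range is assumed. Let N0 be the number of patients who meet every other criterion, including consent, and r the share of them who also meet item 4. Then n = N0 × r, and the ratio of interval widths is sqrt(N0/n) = 1/sqrt(r), whatever N0 is.

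The 95% margin is 1.96 × sqrt(p(1 − p)/n), assuming no censoring before the time point. Inputs for p come from the Protocol's background text:

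- Overall survival: about 75% at 5 years, so p = 0.75.
- Disease-free survival: local recurrence 60%, metastasis 20–25%. Any recurrence is at least 60% (every metastasis in a patient with local recurrence) and at most 60 + 25 = 85% (no overlap). The share free of disease is therefore 15–40%. The Protocol attaches no time point to these rates.

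N0 below 200 allows for losses to consent, since the Informed Consent section expects that some eligible subjects may have died.

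| | r = 100% | 90% | 75% | 50% | 25% |
|---|---|---|---|---|---|
| Width ratio 1/sqrt(r) | 1.00 | 1.05 | 1.15 | 1.41 | 2.00 |
| p = 0.75, N0 = 200 (± points) | 6.0 | 6.3 | 6.9 | 8.5 | 12.0 |
| p = 0.75, N0 = 150 | 6.9 | 7.3 | 8.0 | 9.8 | 13.9 |
| p = 0.75, N0 = 100 | 8.5 | 8.9 | 9.8 | 12.0 | 17.0 |
| p = 0.40, N0 = 200 | 6.8 | 7.2 | 7.8 | 9.6 | 13.6 |
| p = 0.15, N0 = 200 | 4.9 | 5.2 | 5.7 | 7.0 | 9.9 |

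Example: N0 = 200 and r = 0.5 give n = 100, and 1.96 × sqrt(0.75 × 0.25/100) = 0.085.

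**4. The same loss expressed as power**

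With 70% survival at 10 years, deaths are about 0.30 × n. For an assumed hazard ratio of 2, two equal groups and two-sided alpha 0.05, Schoenfeld's formula gives about 77% power at n = 200 (60 deaths), 72% at n = 180 (54 deaths) and 48% at n = 100 (30 deaths). The hazard ratio and the equal split are assumptions; the Protocol states neither.

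**The case against.** The strongest reply is that the design is staged: a 50-gene panel in a few cases, then targeted validation by Sanger and digital PCR in every case that passed the inclusion criteria. Study Design names all three methods without a limit, and the validation sentence can be read this way. Every patient would then need adequate tissue, and items 3 and 4 would fit. This reading cannot be excluded. It is less natural, for the reasons given in the comparison of sections, and if it is intended the Objective needs correcting and the 200 restating. The text has to change either way.

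Other objections carry different weight:

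- *Molecular analysis might include immunohistochemistry, which is planned for all.* Study Design names the two separately, so this does not explain item 4.
- *Requiring tissue from everyone keeps the survival cohort and the molecular series in one population.* True, but the molecular series is limited by tissue in any case. A comparison of the two groups deals with this without shrinking the survival cohort.
- *The loss may be close to nil.* Patients with signed biobank consent plausibly have stored tissue, and the archive section says material is stored. This stands as a possibility. The Protocol gives no count, and the cases span 1993 to 2017.
- *The figures measure precision, while the more serious worry is selection, and any exclusion widens intervals.* This stands. The Protocol sets no precision or power target that would be missed, and bias cannot be quantified from it.

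**Conclusion.** The concern holds. The inclusion list makes an assay-specific tissue condition binding on the whole cohort, while the Objective and Material and Methods limit that assay to a subset. That the sections need reconciling is certain. That patients are wrongly excluded depends on the subset reading, which is the more natural one but not the only one.

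The size is unknown. At 90% retention the loss of precision is negligible; at 50%, intervals are 41% wider, for example ±8.5 instead of ±6.0 points on 75% five-year survival with 200 otherwise eligible patients. These figures rest on assumed retention and no censoring. The direction of any selection cannot be told from the Protocol. The point should be corrected because the loss is avoidable and the change is cheap. Confidence is medium.

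**What to change.** If mutation analysis is meant for a subset:

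1. Make item 4 and the molecular part of item 3 conditions for the molecular series only.
2. Define the main survival cohort as retrieved cases with slides or blocks sufficient for histology and immunohistochemistry that meet items 5 and 6, both unchanged.
3. State in Study Design and Material and Methods which cases get NGS, Sanger sequencing and digital PCR, and which cases the validation sentence covers.
4. Report the number lost at each criterion, and compare the molecular series with the remaining patients on grade, size, treatment era and outcome.

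If Sanger sequencing and digital PCR are meant for every included case, say so, keep item 4, bring the Objective into line, and restate the 200 as the number expected to meet items 3 to 6.

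The cost is a rewording of two inclusion items, Study Design and one sentence of Material and Methods. Review of records, imaging and histology is already planned for all retrieved cases. The extra work is some additional immunohistochemistry and a second analysis set to report. Selection by tissue availability does not vanish; it moves from the whole cohort to the molecular series, which is why the comparison in step 4 is needed. Because the consent criteria stay, the number of patients recovered may be small.
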